### 15.4.2. Study Phases

A study phase will start when the first dose for that phase is taken. The phase will end at either:

- The day before the subsequent phase starts
- The end of the follow up visit (note, this is 16 weeks after the last dose)

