3. OBJECTIVES, ENDPOINTS AND ESTIMANDS

Objectives	Endpoints
Primary	

 To evaluate the safety and tolerability of repeat doses of GSK2831781 during the Double-Blind Induction Phase. To characterise the efficacy dose-response of GSK2831781 during the Double-Blind Induction Phase. 	
 Incidence of adverse events and serious adverse events during the Double-Blind Induction Phase. Incidence of findings of potential clinical importance¹ during the Double-Blind Induction Phase for: 
 Vital signs. Clinical laboratory values (haematology, clinical chemistry and urinalysis). QTc. Change from baseline in Complete 4-domain Mayo score² at Week 10.
Secondary	

 To evaluate the safety and tolerability of repeat doses of GSK2831781 during the Double-Blind Extended Treatment Phase. 	
 Incidence of adverse events and serious adverse events in the Double-Blind Extended Treatment Phase. Incidence of findings of potential clinical importance⁵ during the Double-Blind Extended Treatment Phase for: 
 Vital signs.

Objectives	Endpoints
	
 ○ Clinical laboratory values (haematology, clinical chemistry and urinalysis). ○ QTc. 
 ● To investigate the effect of repeat doses of GSK2831781 on clinical efficacy including endoscopic mucosal healing during the Double-Blind Induction Phase. ● Adapted Mayo endoscopic score of 0 or 1 at Week 10. ● Adapted Mayo clinical remission³ at Week 10. ● Adapted Mayo clinical response³ at Week 10. ● Symptomatic remission⁴ over time. ● Change from baseline in partial Mayo score over time. ● Change from baseline in Adapted Mayo endoscopic score and Ulcerative Colitis Endoscopic Index of Severity (UCEIS) at Week 10.

 ● To investigate the effect of repeat doses of GSK2831781 on UC histologic disease activity during the Double-Blind Induction Phase. 	
 ● Histological severity as determined by the Robarts Histopathology Index at Week 10. ● Histological severity as determined by the Nancy Histological Index at Week 10. ● Histological severity as determined by the Geboes Histological Index at Week 10.

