6.6.1.1. Corticosteroids

Oral corticosteroids are allowed up to a maximum dose of 20 mg/day prednisolone (or equivalent, as detailed in the SRM) on entry to the study, providing they have not been commenced, or the dose altered, within two weeks prior to the baseline endoscopy. The dose of corticosteroids should not change between the baseline endoscopy and Week 12. A dose increase as rescue therapy for UC constitutes an individual stopping criterion (see Section 7.1.1). If the dose of corticosteroid needs to be reduced due to a safety concern, this should be documented appropriately.

A corticosteroid taper is mandatory from Week 12 for participants who are Responders at the Induction Assessment. Non-Responders at Induction who commence Open Label treatment and subsequently attain response (determined following a centrally read endoscopy at Week 22) will undergo corticosteroid taper from Week 24. For Responders, corticosteroids should be tapered according to the following regimen:

- For prednisolone doses >10 mg/day (or equivalent), the dose should be reduced from Week 12 at a rate of 5 mg/week (or equivalent) until a 10 mg/day dose is reached.
- For prednisolone doses ≤ 10 mg/day (or equivalent), or once a 10 mg/day dose (or equivalent) is achieved by tapering, the dose should be reduced at a rate of 2.5 mg/week (or equivalent) until discontinuation.
- Where the initial steroid dose is such that tapering by the above regimen would be challenging because of medicine formulation, it is acceptable for the first step of the taper to be down to a dose that subsequently allows a taper by the above parameters. However, this initial reduction should be by no more than 5 mg prednisolone

equivalent (if initial prednisolone equivalent dose is >10 mg/day) or by 2.5 mg (if initial prednisolone equivalent dose is ≤ 10 mg/day).

- For participants who cannot tolerate the corticosteroid taper without recurrence or exacerbation of clinical symptoms, corticosteroids may be increased up to a maximum of the original dose at the start of the Induction Phase (but should not exceed the baseline dose). In such cases, the tapering regimen above must be reinitiated within 2 weeks of the dose increase. Following two unsuccessful attempts at corticosteroid taper, the patient may re-escalate doses of corticosteroid up to the baseline level.

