9.4. Statistical Analyses

The Induction Phase and Extended Treatment Phase will be reported separately, where the primary and secondary analyses are based on the Weeks 0-10 of the Induction Phase.

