#### **Screening and Post dose records:**

The post-dose records will be summarized under the last study phase in which participants received a dose. The visit windowing algorithm will be based on the following:

1. CRF assessments/events collected after ‘Last Dose Date + 16 Weeks (+ 7 days)’ (i.e. post-treatment study phase) will not be analysed/summarised. These records will only be listed.

2. For CRF assessments/events collected after Last Dose Date but before ‘Last Dose Date + 16 Weeks (+ 7 days)’:
  - a) All records collected in event datasets will be summarized as well as listed (e.g. AE, CM).
  - b) All records collected for any other assessments will be included for ‘Worst-Case’ summaries (e.g. LABs, Mayo score/endpoints etc).
  - c) Unless stated otherwise, all records for any other assessments will be included in visit-based summaries as described in two scenarios below –
    - i. The visits collected in the same study phase will be summarized against the visit in CRF or using windowing RAP algorithm for ‘Unscheduled’.
    - ii. The visits collected in subsequent study phases will be windowed as ‘Follow-up IND/ETP’ visit (even CRF collected scheduled visits will be mapped). For summaries, the latest assessment among ‘Follow-up IND/ETP’ will be used.

Note that after the final visit (Week 30 / OL Week 42) the next visit would be the Follow-Up and it is not expected that a participant would have an Early Withdrawal visit after these visits.

Target Day	Analysis Window (Days)		Analysis Timepoint
	Beginning Timepoint	Ending Timepoint	
Note: Windowing applies to all domains except Extra Intestinal Manifestations of UC.			
1	1	2	DAY 1
15	3	22	WEEK 2
29	23	36	WEEK 4
43	37	57	WEEK 6
71	58	A day prior to participant's first dose of next phase. For participants who do not take a subsequent dose, maximum of 'Week 10 dosing date +3' and day 85	WEEK 10
99* (First Dose of Period + 1)	Participant's first dose of ETP	102* (First dose of Period + 4)	WEEK 14
127* (First dose of Period + 29)	103* (First dose of Period + 5)	141* (First dose of Period + 43)	WEEK 18
155* (First dose of Period + 57)	142* (First dose of Period + 44)	169* (First dose of Period + 71)	WEEK 22

Target Day	Analysis Window (Days)		Analysis Timepoint
	Beginning Timepoint	Ending Timepoint	
183* (First dose of Period + 85)	170* (First dose of Period + 72)	197* (First dose of Period + 99)	WEEK 26

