#### 15.4.2.1. Study Phases for Adverse Events

If a participant discontinues treatment (i.e. the 'study treatment discontinuation' form has been completed) but continues to attend visits AEs will be associated with the study phase until 16 weeks (+7 days) after the last dose. If an AE onset date is during the post-treatment period the AE will not be summarised against a study phase.

If an AE onset date is in one phase and resolution date is in a subsequent phase, the AE will be associated with the phase in which the AE starts. AEs that cross phases where the maximum severity is greater than the severity at onset will be listed separately.

Following the standard rules for summarising AEs, if an AE of a category repeats in the same study phase this will be counted once in that phase, however if the same AE repeats in a subsequent phase, it will be counted in both the first phase and the subsequent phase because AEs in each study phase are summarised in separate tables.

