3.64.	Safety ETP	VS1	As above for Extended Treatment Phase		SAC
3.65.	Safety OL I	VS1	As above for Open Label Induction Phase		SAC
3.66.	Safety OL ETP	VS1	As above for Open Label Extended Treatment Phase		SAC
3.67.	Safety	VS7	Summary of Worst-Case Vital Signs Results by PCI Criteria Post-Baseline Relative to Baseline for Induction Phase	IDS Note: Adjust shell to include temperature (required for disclosure). Use footnote and title of middle category from VS7 (i.e. change 'normal' to 'within range') Include change from baseline for Systolic Blood Pressure, Diastolic Blood Pressure and Heart Rate	SAC
3.68.	Safety ETP	VS7	As above for Extended Treatment Phase		SAC
3.69.	Safety OL I	VS7	As above for Open Label Induction Phase		SAC

Safety: Tables					
No.	Population	IDSL / Example Shell	Title	Programming Notes	Deliverable [Priority]
3.70.	Safety OL ETP	VS7	As above for Open Label Extended Treatment Phase		SAC
Immunogenicity					
3.71.	Safety	sb240563/mid20 5050/final_02/ Table 3.38	Summary of Confirmed Positive Binding Antibody by Visit for Induction Phase		SAC
3.72.	Safety ETP	sb240563/mid20 5050/final_02/ Table 3.38	As above for Extended Treatment Phase		SAC
3.73.	Safety OL I	sb240563/mid20 5050/final_02/ Table 3.38	As above for Open Label Induction Phase		SAC
3.74.	Safety OL ETP	sb240563/mid20 5050/final_02/ Table 3.38	As above for Open Label Extended Treatment Phase		SAC
3.75.	Safety	sb240563/mid20 5050/final_02/ Table 3.39	Summary of Confirmed Positive Neutralising Antibody by Visit for Induction Phase		None

Safety: Tables					
No.	Population	IDSL / Example Shell	Title	Programming Notes	Deliverable [Priority]
3.76.	Safety ETP	sb240563/mid20 5050/final_02/ Table 3.39	As above for Extended Treatment Phase		None
3.77.	Safety OL I	sb240563/mid20 5050/final_02/ Table 3.39	As above for Open Label Induction Phase		None
3.78.	Safety OL ETP	sb240563/mid20 5050/final_02/ Table 3.39	As above for Open Label Extended Treatment Phase		None
Adverse Events – Additional Summaries					
3.79.	Safety	AE17	Summary of Exposure Adjusted Incidence Rates for Adverse Events in Induction Phase	For selected Preferred Terms – 1) All Preferred terms in System Organ class of Infections and Infestations 2) Preferred Term – Colitis Ulcerative	SAC
3.80.	Safety	TTE1	Summary of Time to Ulcerative Colitis Adverse Event in Induction Phase	For selected Preferred Terms – 1) Preferred Term – Colitis Ulcerative	SAC

Safety: Tables					

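### Crude induction AE and SAE incidence is counted over a period that depends on Week 10 response and on discontinuation; a common-window display should carry the between-arm comparison

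*SAP*

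**What the plan says.** Protocol section 3 makes "Incidence of adverse events and serious adverse events during the Double-Blind Induction Phase" a primary endpoint. SAP 15.4.2 starts a phase at its first dose and ends it at one of two points: "The day before the subsequent phase starts", or "The end of the follow up visit (note, this is 16 weeks after the last dose"). For participants who stop treatment but keep attending, SAP 15.4.2.1 adds that "AEs will be associated with the study phase until 16 weeks (+7 days) after the last dose". The post-dose rules in SAP 15.3.1 confirm that such events enter the summaries: "All records collected in event datasets will be summarized as well as listed (e.g. AE, CM").

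Under the Protocol 1.2 schema, Week 10 non-responders take their first open-label dose at Week 12 and responders their first SC dose at Week 14. Protocol 6.6.1.1 states: "A corticosteroid taper is mandatory from Week 12 for participants who are Responders at the Induction Assessment". Protocol 4.1.1 limits this to participants to whom a taper applies, that is, those taking corticosteroids.

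Protocol 9.4 says that "the primary and secondary analyses are based on the Weeks 0-10 of the Induction Phase".

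The induction AE and SAE displays in SAP 15.12.7 (Tables 3.1, 3.2, 3.6, 3.10 and 3.19) are crude subject incidence. Figure 3.1 (SAP 15.12.8) shows relative risks for each active dose, and for the doses combined, against placebo. Exposure-adjusted rates (Table 3.79) cover only infections and Colitis Ulcerative. Table 3.80, "Summary of Time to Ulcerative Colitis Adverse Event in Induction Phase", covers only Colitis Ulcerative.

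**The concern.** Crude incidence is comparable between arms only if participants are observed for similar periods, or if the periods differ for reasons unrelated to treatment. Here the end of the window is fixed by response at Week 10 and by whether the participant goes on to further dosing, and treatment may affect both. If 450 mg and placebo differ in response or discontinuation, their AE percentages can differ even when the risk per day is the same.

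The conditions within the window differ too. Days 85 to 98 exist only for responders and for participants who take no next-phase dose. For responders on corticosteroids those days are taper days, whereas open-label responders taper from Week 24, outside this phase. At stake is how a reader interprets the first primary endpoint and the relative risks plotted from it.

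**Working it through.** **Reproducing the calendar.** SAP 15.3.1 sets the target day for week w at 7w + 1. Week 12 is Day 85, Week 14 is Day 99 and Week 26 is Day 183. Sixteen weeks after the Week 26 dose is 183 + 112 = 295, the Week 42 day in the schedule of activities. The induction doses at Weeks 0, 2, 6 and 10 fall on Days 1, 15, 43 and 71.

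**Window for each participant** (from Day 1, so the end day equals the length):

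| Path | Last day counted |
|---|---|
| Non-responder, open label at Week 12 | 85 − 1 = 84 |
| Responder, SC at Week 14 | 99 − 1 = 98 (98/84 = 1.17) |
| Last dose Week 2, no next phase | 15 + 112 = 127; with +7 days, 134 |
| Last dose Week 6, no next phase | 43 + 112 = 155; with +7 days, 162 |
| Last dose Week 10, no next phase | 71 + 112 = 183; with +7 days, 190 |

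The last three rows are upper limits, reached only if the participant is followed to the end. Taper days inside induction for responders on corticosteroids: 98 − 84 = 14.

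**Arm means.** The documents give neither response nor discontinuation rates by arm, so these are assumptions. With response r, a proportion d taking no next-phase dose, and end day D for that proportion: mean = d·D + (1 − d)·[98r + 84(1 − r)].

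- Response alone (d = 0): r = 0.30 gives 88.2 days and r = 0.60 gives 92.4; 92.4/88.2 = 1.048.
- D = 162, placebo r = 0.30, d = 0.20: 32.4 + 0.80 × 88.2 = 103.0. For 450 mg, r = 0.50, d = 0.05: 8.1 + 0.95 × 91.0 = 94.6.
- As above with placebo d = 0.10: 16.2 + 0.90 × 88.2 = 95.6 v 94.6, almost equal.
- D = 190, r = 0.30 in both arms, d = 0.20 on placebo v 0.05 on active: 108.6 v 93.3, active/placebo ratio 0.86.
- D = 190, placebo r = 0.30, d = 0.05 v active r = 0.50, d = 0.15: 93.3 v 105.8, ratio 1.13.

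The direction therefore depends on which arm stops more.

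**Effect on crude incidence under one constant hazard.** Take an AE with 30% incidence by Day 84 (assumed). Incidence by day t is 1 − 0.70^(t/84): 34.0% at 98 days and 49.7% at 162.

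- Response 30% v 60%, no discontinuation: 0.30 × 34.0 + 0.70 × 30.0 = 31.2% v 0.60 × 34.0 + 0.40 × 30.0 = 32.4%.
- The 103.0 v 94.6 day scenario: placebo 0.20 × 49.7 + 0.80 × 31.2 = 34.9%; 450 mg 0.05 × 49.7 + 0.95 × 32.0 = 32.9%. That is about 2 points with no difference in risk.

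**With a common cut at Day 84.** Nominal windows are 84 days for everyone, scheduled taper days fall to 0, and the same AE shows 30.0% in every arm.

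**The case against.** The strongest reply is that the boundary was chosen. The Amendment 3 history (Protocol 10.13.3) explains that induction safety data are to be reported up to the start of dosing in the following phase. A reader might infer from Protocol 9.4 that the SAP departs from the protocol. The documents do not support that: the Weeks 0-10 sentence was simply not aligned with the safety reporting period, and a literal stop at Week 10 would drop events after the fourth dose.

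Nor is the tail simply time off drug. Protocol 4.2 justifies 16 weeks as washout. After 5 mg/kg, the mean concentration was still 0.5 µg/mL 12 weeks after dosing, and only 2 of 6 participants were below quantification. SAP 15.4.1 classes the period as on-treatment. Late events there belong in the safety record.

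The taper reaches only responders on corticosteroids, and Protocol 10.3.1 excludes expected disease symptoms from AEs unless they are more severe than expected, so many mild flares would not be counted. Safety is not formally tested. A 2-point shift is also small beside sampling error: at the planned 68 v 48 participants and incidence near 34%, the standard error of the difference is √[0.34 × 0.66 × (1/68 + 1/48)] ≈ 0.09, or about 9 points.

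All of this stands, and it argues for keeping the phase-based tables. It does not make the windows comparable. Table 3.79 helps only for infections and Colitis Ulcerative, and for event-free participants its denominator adds a dose-specific number of days that SAP 15.6.2 does not define. Table 3.80 handles unequal follow-up in principle. However, non-responders who switch leave at about Day 84, so later events come only from responders and from participants with no next-phase dose. The censoring rules are not in the SAP text, and the mock shells are a separate document.

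**Conclusion.** The point holds as a limitation of the crude comparison. The SAP's rule makes the induction AE window differ between participants according to response and discontinuation, and the main AE and SAE tables and Figure 3.1 do not adjust for it. That much follows from the text and the visit calendar.

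The size at arm level is likely modest and cannot be settled from the documents. It is about 5% in mean follow-up from a 30% v 60% response difference. Under assumed discontinuation of 5% to 20% per arm, the ratio of mean windows ran from 0.86 to 1.13 in the scenarios above, and one scenario nearly cancelled. The incidence figures assume a constant hazard and complete follow-up to the end of each window.

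A reader might infer that the primary safety comparison is biased in a known direction, or that the study's termination biases it further. Neither is supported. The direction depends on unknown rates. Termination was the sponsor's decision, not an effect of treatment, and the documents show no difference between 450 mg and placebo in how many participants it stopped during induction. It can lengthen individual windows, but that is all that can be said. This is a worthwhile, inexpensive addition, not a reason to replace the planned tables.

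**What to change.** Keep the phase-based tables as planned. Add a prespecified common-window display of AEs and SAEs, and of UC events alongside Table 3.80. For every participant, count onsets from first dose to the earlier of Day 84 and the day before the first next-phase dose. State that between-arm comparison of induction AEs, including the Figure 3.1 relative risks, rests on this display. Day 84 keeps 13 days after the Week 10 dose and stops before the scheduled taper and the switch to open label. Separately, reconcile the Weeks 0-10 wording in Protocol 9.4 with the safety reporting period.

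The cost is one date cut on data already collected and one extra set of tables. Events after Day 84 would appear only in the phase-based tables. The cut is not perfectly equal: the ±5-day visit window allows open-label dosing from Day 80, so some non-responders' windows would end at Day 79, a residual difference of up to about 5 days. It also cannot restore observation for anyone who leaves the study before Day 84.

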#### 15.4.2.1. Study Phases for Adverse Events

If a participant discontinues treatment (i.e. the 'study treatment discontinuation' form has been completed) but continues to attend visits AEs will be associated with the study phase until 16 weeks (+7 days) after the last dose. If an AE onset date is during the post-treatment period the AE will not be summarised against a study phase.

If an AE onset date is in one phase and resolution date is in a subsequent phase, the AE will be associated with the phase in which the AE starts. AEs that cross phases where the maximum severity is greater than the severity at onset will be listed separately.

Following the standard rules for summarising AEs, if an AE of a category repeats in the same study phase this will be counted once in that phase, however if the same AE repeats in a subsequent phase, it will be counted in both the first phase and the subsequent phase because AEs in each study phase are summarised in separate tables.

**15.4.2.2. Study Phases for Concomitant Medication**

Study Phase	Definition
Prior	If medication end date is not missing and is before first dose of study treatment.
Concomitant	Any medication that is not a prior and that has start date before or during the on-treatment phase.
Post-Treatment	Any medication that has a start date after the end of the on-treatment phase.

**15.4.3. Treatment Emergent Flag for Adverse Events**

Flag	Definition
Treatment Emergent	

• If AE onset date (and time) is after treatment start date (and time) and during the On-treatment period, the AE will be considered Treatment Emergent.

**NOTES:**

- If the study treatment stop date is missing, then the AE will be considered to be On-Treatment.
- Time of study treatment dosing and start/stop time of AEs should be considered, if collected.

## 15.5. Appendix 5: Data Display Standards & Handling Conventions

### 15.5.1. Reporting Process

Software	

 
The currently supported versions of SAS software will be used.
 
	
Reporting Area	
HARP Server	: uk1salx00175
HARP Compound	: \arenv\arprod\gsk2831781\
Reporting effort type	HARP path
N30 Dry Run	: \arenv\arprod\gsk2831781\mid204869\data_look_01
N30	: \arenv\arprod\gsk2831781\mid204869\safety_01
IA3 Dry Run 1	: \arenv\arprod\gsk2831781\mid204869\data_look_02
IA3 Dry Run 2	: \arenv\arprod\gsk2831781\mid204869\data_look_04
IA3 Headline	: \arenv\arprod\gsk2831781\mid204869\internal_02
Final CSR Dry Run	: \arenv\arprod\gsk2831781\mid204869\data_look_05
Final CSR	: \arenv\arprod\gsk2831781\mid204869\final_01
Analysis Datasets	

 
Analysis datasets will be created according to CDISC standards (SDTM IG Version 3.2 & ADaM IG Version 1.1. If the Study Data Standardization Plan (SDSP) exists for a study, ensure the CDISC versions are consistent.
 
	
Generation of RTF Files	

 
RTF files will be generated for the primary completion and final SAC described in the RAP.
 
	

## 15.5.2. Reporting Standards

General	

 
The current GSK Integrated Data Standards Library (IDSL) will be applied for reporting, unless otherwise stated (IDSL Standards Location:  https://spope.gsk.com/sites/IDSLLibrary/SitePages/Home.aspx):           
 
4.03 to 4.23: General Principles
 
5.01 to 5.08: Principles Related to Data Listings
 
6.01 to 6.11: Principles Related to Summary Tables
 
7.01 to 7.13: Principles Related to Graphics
 
 
 
Do not include subject level listings in the main body of the GSK Clinical Study Report. All subject level listings should be located in the modular appendices as ICH or non-ICH listings
 
	
Formats	

 
GSK IDSL Statistical Principles (5.03 & 6.06.3) for decimal places (DP's) will be adopted for reporting of data based on the raw data collected, unless otherwise stated.
 
Numeric data will be reported at the precision collected on the eCRF.
 
The reported precision from non eCRF sources will follow the IDSL statistical principles but may be adjusted to a clinically interpretable number of DP's.
 
	
Planned and Actual Time	

 
Reporting for tables, figures and formal statistical analyses:           
 
Assessment windows will allocate actual visit time to planned visits which will be used in summary figures, summaries, statistical analyses and calculation of any derived parameters, unless otherwise stated.
 
The impact of any major deviation from the planned assessment times and/or scheduled visit days on the analyses and interpretation of the results will be assessed as appropriate.
 
 
 
Reporting for Data Listings:           
 
Planned and actual time relative to study drug dosing will be shown in listings (Refer to IDSL Statistical Principle 5.05.1).
 
Unscheduled or unplanned readings will be presented within the subject's listings.
 
 
 
	
Treatment Actually Received	

 
If a participant has been dosed at more than one dose level within a phase (i.e. they have been incorrectly dosed) then their 'actual' treatment allocation will be defined as the highest dose received.
 
	
Treatment	

 
In listings where results are reported per visit, the treatment received in each phase will be associated with the visits in that phase. Where order is 'by treatment' the order will be based on treatment received in the induction phase.
 
Note that summaries are, in general, reported separately for each study phase whereas, in general, there will be a single listing across all phases.
 
	
Unscheduled Visits	

 
Observations from Unscheduled visits will follow the rules for assessment windows but will not be separately summarised as 'Unscheduled' in summary tables or figures.
 
All unscheduled visits will be included in listings.
 
	
Descriptive Summary Statistics	
Continuous Data	Refer to IDSL Statistical Principle 6.06.1
Categorical Data	N, n, frequency, %

Graphical Displays	

 
• Refer to IDSL Statistical Principles 7.01 to 7.13.
 
	

